Adverse event or intercurrent illness	
Subjects must discontinue early for any intolerable adverse event that may lead to undue risk if study treatment were continued, such as the following:
 
 • Life-threatening symptoms, including anaphylaxis resulting in hypotension, neurologic compromise, or mechanical ventilation related to study treatment or food challenge. • Severe dose-related symptoms that require intensive therapy (per investigator assessment, but may include interventions such as IV epinephrine, intubation, or admission to an intensive care unit) or are recurrent. 
Subjects must discontinue early for any adverse event that meets the early discontinuation criteria for study product tolerability or delays as follows:
 
 • Tolerability of study product: 
 – Dose-limiting or moderate symptoms at ≤ 1 mg or severe symptoms at any dose on initial dose-escalation day 1; dose-limiting, moderate, or severe symptoms on initial dose-escalation day 2 – Unable to reach the 300 mg/day dose within 40 weeks of up-dosing • Use of rescue medications: 
 – Treatment with epinephrine, beta-agonist, oxygen, IV fluids, > 2 doses of antihistamines, and/or glucocorticosteroids at ≤ 1 mg study product or for severe symptoms at the 2 mg dose on initial dose-escalation day 1 or 2 – Treatment with 3 or more doses of epinephrine for an event of dose-related symptoms anytime • Dose adjustment of study product: 
 – Unable to escalate the dose level after 3 consecutive failed attempts with at least 2 weeks between each escalation attempt – Unable to tolerate 3 attempts at dose reduction after mild or moderate symptoms, or unable to tolerate 1 attempt at dose reduction after severe symptoms • Missed ≥ 15 consecutive days of study product dosing due to any circumstances (eg, as part of the treatment for an intercurrent adverse event). Missed doses per dose adjustment guidelines in Section 8.7.3.2 are allowed. 
Subjects must discontinue early for any intolerable adverse event that cannot be ameliorated using adequate medical intervention or that in the opinion of the investigator or sponsor may lead to undue risk if study treatment were continued, such as the following:
 
 • Poor control or persistent activation of secondary atopic disease (eg, atopic dermatitis, asthma). • Development of biopsy-documented eosinophilic esophagitis.

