8.7.3 Dose Adjustment of Study Product for Allergic Reactions

[figure not shown]
8.7.3.1 Dose Adjustment of Study Product During Initial Dose Escalation (Days 1 and 2)

Actions that may be taken with study product for allergic reactions occurring on day 1 of initial dose escalation are guided by the severity of the allergic reactions and include the following:

- Extend the time interval between study product doses (up to an additional 30 minutes) without any additional treatment.
- Initiate enhanced clinical monitoring (eg, more frequent vital sign monitoring [including respiratory rate], auscultation, oxygen saturation level).
- Treat with antihistamine and resume study product dose escalation within 60 minutes after the previous dose, if assessed as safe.
- Treat with epinephrine, beta-agonist, oxygen, IV fluids, > 2 doses of antihistamines, and/or glucocorticosteroids as necessary. Stop the initial dose escalation and discontinue the subject early from the study if these rescue medications are used at ≤ 1 mg study product or for severe symptoms at the 2 mg dose ([Section 5.3](#)).
- Stop the initial dose escalation and discontinue the subject early from the study.

The process algorithm for actions to be taken with study product dosing and treatment for acute symptoms on initial dose-escalation day 1 is shown in [Figure 2](#) and described in [Table 12](#). The same process algorithm for actions to be taken with study product dosing and treatment for acute symptoms is to be followed for allergic reactions occurring on day 2 of initial dose escalation, with the exception that only 1 dose will be administered on day 2.

Figure 2: Management of Study Product Dosing for Allergy Symptoms on Initial Dose-Escalation Day 1

Assess dose tolerability per [Section 8.7.1.1](#).

Table 12: Description of Actions to Be Taken With Study Product Dosing for Allergy Symptoms on Initial Dose-Escalation Day 1

Symptoms	Actions

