Mild	
For oral/pharyngeal pruritus occurring in isolation, advance to the next dose of study product in 30 minutes.
 
For other mild symptoms, either:
 
 Advance to the next dose of study product in 30 to 60 minutes. Treat with antihistamine, then resume dose escalation within 60 minutes after the previous dose if signs and symptoms resolve to minimal or residual, and the investigator considers continued dosing to be safe. 
If only 1 or 2 doses of antihistamine are used to treat mild symptoms, the initial dose escalation may continue.
 
If a second medication (eg, epinephrine or a beta-agonist) or > 2 doses of antihistamines are needed, stop the initial dose escalation and discontinue the subject early from the study, even if the symptoms are assessed as mild.
 
Use of epinephrine, although unlikely to be used to treat mild dose-related symptoms, will stop the initial dose escalation and discontinue the subject early from the study.

Moderate	
For moderate symptoms not worsening in intensity or distribution over time, the investigator may take a stepwise approach to treatment. Treatment may be initiated immediately or after observation. If the first action is observation, observation should not exceed 30 minutes before starting treatment if symptoms have not resolved. Initiate treatment with antihistamines or administer epinephrine immediately as appropriate. Initiate other therapies sequentially or concurrently per investigator judgment.
 
For moderate symptoms occurring at ≤ 1 mg study product, stop the initial dose escalation and discontinue the subject early from the study.

Severe	
For severe symptoms at any dose, administer the appropriate rescue medications and treatment per standard of care. Stop the initial dose escalation and discontinue the subject from study early.

Life-threatening	
For life-threatening symptoms at any dose, administer the appropriate rescue medications and treatment per standard of care. Stop the initial dose escalation and discontinue the subject from study early.

Assess dose tolerability per [Section 8.7.1.1](#).

Treatment with epinephrine, beta-agonist, oxygen, IV fluids, > 2 doses of antihistamines, and/or glucocorticosteroids at ≤ 1 mg study product or for severe symptoms at the 2 mg dose on initial dose-escalation day 1 or 2 will stop the initial dose escalation and discontinue the subject early from the study ([Section 5.3](#)).

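### Table 12's mild-symptom row discontinues a subject who needs further rescue medication at any day-1 dose; its own note, Sections 5.2.3.1 and 8.7.3.1, and Table 4 do not do so for mild symptoms at 2 mg

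*Protocol*

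**What the plan says.** Day 1 has five ascending doses: 0.2, 0.4, 0.8, 1 and 2 mg (Protocol Section 5.2.3.1, Table 1). Only the last exceeds 1 mg. Several places say when rescue medication ends a subject's participation.

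**Table 12, mild row (Section 8.7.3.1).** One or two antihistamine doses allow escalation to go on. Beyond that, when a second drug or more than 2 antihistamine doses are needed, the instruction is to "stop the initial dose escalation and discontinue the subject early from the study, even if the symptoms are assessed as mild". A separate sentence covers epinephrine: "Use of epinephrine, although unlikely to be used to treat mild dose-related symptoms, will stop the initial dose escalation and discontinue the subject early". Neither sentence names a dose.

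**Table 12, moderate row.** This row does name a dose: "For moderate symptoms occurring at ≤ 1 mg study product, stop the initial dose escalation and discontinue the subject early from the study".

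**Note under Table 12.** Epinephrine, beta-agonist, oxygen, IV fluids, more than 2 antihistamine doses or glucocorticosteroids end participation when used "at ≤ 1 mg study product or for severe symptoms at the 2 mg dose on initial dose-escalation day 1 or 2 will stop".

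**Section 8.7.3.1, bullet on the same treatments.** Stop and discontinue "if these rescue medications are used at ≤ 1 mg study product or for severe symptoms at the 2 mg dose".

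**Table 4 (Section 5.3).** The rescue-medication criterion carries the same limit: "and/or glucocorticosteroids at ≤ 1 mg study product or for severe symptoms at the 2 mg dose on initial dose-escalation day 1 or 2".

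**Section 5.2.3.1 and Table 2, footnote [1].** These again give the same limit. The Day 2 text adds that a subject who tolerated at least 1 mg, and whose symptoms at 2 mg were mild or moderate at worst, comes back for the confirmatory 1 mg dose. The Synopsis and Section 3.1 agree.

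**The concern.** A subject with mild symptoms after the 2 mg dose who is given epinephrine, a beta-agonist as a second drug, or a third antihistamine dose is discontinued under the Table 12 row. Under the other passages that subject returns the next day. The two instructions exclude each other.

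The ordering by severity is also reversed at this dose. A mild reaction at 2 mg treated with epinephrine ends participation, while a moderate reaction at 2 mg treated with the same drug does not. The protocol gives no reason for this.

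Early discontinuation is permanent cessation of study product (Section 5.3), and a subject who discontinues before the exit food challenge is a nonresponder in the primary ITT analysis (Section 10.5.1). Which passage a site follows can therefore fix that subject's primary outcome on day 1. This is also a safety decision point in a first-in-human study at about 30 sites.

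**Working it through.** The protocol gives no figure to reproduce for this point. The check sets the rules side by side for every combination of dose and severity, for a subject given epinephrine, a second drug, or more than 2 antihistamine doses on day 1.

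| Case | Table 12 row | Table 12 note, Section 8.7.3.1 bullet, Table 4, Section 5.2.3.1 | Agree? |
|---|---|---|---|
| Mild, 0.2 to 1 mg | Discontinue | Discontinue | Yes |
| Mild, 2 mg | Discontinue (no dose limit) | Rescue rule not triggered; Section 5.2.3.1 sends the subject to day 2 | **No** |
| Moderate, 0.2 to 1 mg | Discontinue | Discontinue | Yes |
| Moderate, 2 mg | Not discontinued | Not triggered; subject goes to day 2 | Yes |
| Severe, any dose | Discontinue | Discontinue | Yes |

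Day 2 raises no further conflict over these drugs, because its only dose is 1 mg.

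**Could another rule discontinue the mild 2 mg case anyway?** Under Section 8.7.1.1, mild symptoms that need epinephrine or 3 or more antihistamine doses do not meet the tolerability criteria, so they are dose-limiting. But Table 4 and Section 5.2.3.1 make dose-limiting symptoms on day 1 a reason to discontinue only at 1 mg or less. That route does not close the gap.

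**Does the mild row carry an implied dose limit?** Table 12 sets dose scope row by row. The moderate row states a limit of 1 mg or less, and the severe and life-threatening rows apply to every dose. The mild row states nothing, and the note beneath has no marker linking it to that row.

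**Size per subject.** Section 10.3 plans 56 subjects on AR201. One responder turned into a nonresponder changes the AR201 rate by 1/56 = 0.0179, or 1.8 percentage points. This is a ceiling, since it supposes the subject would otherwise have responded. If such a subject had the 60% response rate assumed in Section 10.3, the expected loss would be 0.60 × 1.8 = 1.1 points. The protocol gives no rate for the event, so no total can be computed.

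**The case against.** The best defence is that the mild row, read in context, concerns doses that have a next step. It speaks of advancing, resuming, continuing and stopping escalation, and nothing follows 2 mg on day 1. The note under the same table deals with exactly these treatments, is not confined to one severity, and states the limit, which also appears in Section 5.2.3.1, Table 2, the Section 8.7.3.1 bullet and Table 4. On this view the reversed ordering shows that the row simply lacks a qualifier, and a medical monitor is available for questions.

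Some of this stands. The limited rule is stated more often, the affected case is narrow, and the reversed ordering follows from the same missing qualifier and is not a second defect. That reactions at 2 mg would fall mainly in the AR201 arm is an inference, not a figure from the protocol.

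It does not remove the conflict. The severe row and the note both speak of stopping escalation for reactions at 2 mg, so that phrase does not exclude the last dose, and discontinuation from the study has full meaning there. No precedence is stated. Section 8.7.3.1 names Figure 2 and Table 12 as the day-1 algorithm, so a site that follows the row is following the protocol. Figure 2 is not reproduced in the text available and could not be checked. It may branch by dose, but the written passages would still disagree.

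**Conclusion.** The concern holds. It is an internal contradiction confined to one case: mild symptoms at the 2 mg day-1 dose treated with epinephrine, a second drug or more than 2 antihistamine doses. The rules agree in every other case.

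The effect on the trial is probably small. The protocol itself calls epinephrine for mild symptoms unlikely, although a beta-agonist added as a second drug or a third antihistamine dose also triggers the row. The ceiling is 1.8 percentage points of AR201 response rate per affected subject, and the number of such subjects is unknown. The point is minor in weight but worth correcting, because the contradiction decides whether a subject is permanently withdrawn and counted as a nonresponder. No view is taken here on which rule is clinically right.

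**What to change.** Reconcile the mild row of Table 12 with the note beneath it, the Section 8.7.3.1 bullet, Section 5.2.3.1, Table 2 footnote [1] and Table 4, so that a single rule governs rescue medication at the 2 mg dose for every severity. Check Figure 2 against the reconciled text. The sponsor and its clinicians decide what the rule is.

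The cost is amendment wording, in one table row or in its counterparts, depending on the rule chosen. The endpoint definition, sample size and analysis method do not change.

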8.7.3.2 Dose Adjustment of Study Product During Up-Dosing and Maintenance

Actions that may be taken with study product dosing for dose-related allergic reactions during up-dosing and maintenance are guided by the severity of the allergic reactions and include the following:

- Administer the next dose of study product at the study site under medical supervision.

- Delay the study product dose escalation an additional 1 to 2 weeks.
- Reduce the study product dose level by 1 or 2 dose levels (study product dose levels are provided in [Table 3](#)).
- Temporarily withhold study product.
- Stop study product dosing and discontinue the subject early from the study ([Section 5.3](#)).

The severity of the symptoms will guide study product dose reductions for both acute and chronic or recurrent symptoms. The process algorithm for dose adjustments for dose-related symptoms occurring at a new dose or dose level given at the study site or for symptoms of a dose-related allergic reaction reported during daily dosing at home is shown in [Figure 3](#) and described in [Table 13](#).

When study product dose-related allergy symptoms occur at home, the subject or parent/caregiver must report the symptoms to the study site to determine whether the next dose should be administered at home or at the study site. Administration of study product at the study site under medical supervision is strongly encouraged any time that acute symptoms are reported, including mild symptoms occurring with a dose that is suspected to be not tolerated.

The dose escalation may be delayed or the dose level reduced if the tolerability of a dose level is uncertain, at investigator discretion ([Section 8.7.1.1](#)).

In general, a reduced dose of study product is to be given at the study site under medical supervision and continued for 1 to 2 weeks at home. The lowest dose level of study product for dose adjustments is 1 mg.

[figure not shown]
Symptomatic treatment should be used to supplement dose reduction and not as a substitute for it. Symptomatic treatment of adverse events should be discontinued before attempting dose re-escalation at the study site. However, if treatment for chronic or recurrent adverse events cannot be withdrawn successfully and the dose level is assessed as tolerated by the investigator, it may be administered concurrently with study product dose re-escalation.

A dose re-escalation attempt should be made within 4 weeks after a dose reduction.

Study product dosing will stop and the subject will discontinue early ([Section 5.3](#)) if any of the following conditions are met for dose adjustment:

- The dose level cannot be escalated after 3 consecutive failed attempts with at least 2 weeks between each escalation attempt.
- The dose reduction cannot be tolerated after 3 attempts to reduce the dose level.

Figure 3: Management of Study Product Dosing for Dose-Related Allergy Symptoms During Up-Dosing and Maintenance

Assess dose tolerability per [Section 8.7.1.1](#).

- [1] Guidelines for dose adjustment after administration of antihistamines and/or epinephrine for dose-related allergy symptoms of any severity are provided in [Table 14](#).
- [2] The actions for moderate symptoms assessed as tolerated are the same as for a dose or dose level associated with mild symptoms assessed as tolerated ([Table 13](#)).

Table 13: Description of Actions to Be Taken With Study Product Dosing for Dose-Related Allergy Symptoms During Up-Dosing and Maintenance

Symptoms	Actions
Mild	
For oral/pharyngeal pruritus occurring in isolation, continue the study product dose level at home for the 2-week dosing interval, unless other symptoms develop.
 
For other mild symptoms and if the study product dose is assessed as tolerated (Section 8.7.1.1), repeat the same dose level the next day, ideally at the study site although it may be given at home.
 
 • If no symptoms occur with the repeated dose, continue the dose level for the 2-week dosing interval. • If mild symptoms occur with the repeated dose and the dose is assessed as tolerated, continue the same dose level or reduce the dose to the previous tolerated dose level for the 2-week dosing interval. 
For other mild symptoms and if the study product dose is assessed as not tolerated (Section 8.7.1.1), the next dose is to be the previous tolerated dose level and given at the study site.
 
 • If the reduced dose is tolerated, continue the dose level for at least 1 to 2 weeks. • If the reduced dose is assessed as not tolerated, the next dose is to be reduced 1 or 2 dose levels and given at the study site. 
 – If the second reduced dose is tolerated, continue this dose level for the 2-week dosing interval. – If the second reduced dose is assessed as not tolerated, discuss early discontinuation with the medical monitor. – If a third reduced dose is considered to be safe after discussion with the medical monitor, give it at the study site under medical supervision. If the dose is assessed as not tolerated, stop study product dosing and discontinue the subject early from the study (Section 5.3). 
For other mild symptoms and if the study product dose tolerability is uncertain, follow the general guidance in this table for chronic or recurrent mild symptoms.

Mild (chronic or recurrent)	
The recurrence of mild dose-related symptoms over several days of dosing at home may suggest that the study product dose level is not tolerated, even if each dose could be assessed as tolerated.
 
 • For symptoms occurring \geq 4 times in a week, give the next dose of study product at the study site to assess tolerability. • For symptoms occurring \geq 7 times during the 2-week dosing interval, the dose level will be considered not tolerated (Section 8.7.1.1). • Recurrent, isolated mild oropharyngeal pruritus occurring \geq 7 times within 2 weeks may not lead to an assessment of not tolerated for the dose level; tolerability of the dose level should be discussed with the medical monitor. 
Other actions that may be taken for chronic or recurrent mild symptoms:
 
 • Continue daily dosing at home at the current dose level. • Repeat the same dose level at the study site to assess tolerability. • Delay the dose escalation by 1 to 2 weeks. • Give the previous tolerated dose level (1 or 2 dose levels lower based on severity of reaction) at the study site. • Stop study product dosing and discontinue the subject early from the study (Section 5.3).

Symptoms	Actions
	
GI symptoms
 
For chronic or recurrent GI symptoms, especially upper GI symptoms, a low threshold for study product dose reduction and for considering early discontinuation is recommended due to the potential for eosinophilic esophagitis.
 
For dose-limiting chronic or recurrent GI symptoms, follow the general guidance in this table based on symptom severity.

Moderate	
Administer the previous tolerated dose of study product at the study site at the time of the next dose.
 
 • If no symptoms occur with the reduced dose, continue that dose level for 2 weeks before attempting re-escalation. • If mild symptoms occur at the reduced dose, follow the guidelines for mild symptoms. • If moderate symptoms occur at the reduced dose, give a second reduced dose (1 or 2 dose levels lower) the next day at the study site. 
 – If the second reduced dose is tolerated, continue that dose level for at least 2 weeks before attempting re-escalation. – If mild symptoms occur with the second reduced dose that is assessed as not tolerated, follow the guidelines for mild symptoms. – If moderate symptoms recur at the second reduced dose, discuss early discontinuation with the medical monitor. 
 ▪ If a third reduced dose is considered to be safe after discussion with the medical monitor, give it at the study site under medical supervision. If the dose is assessed as not tolerated, stop study product dosing and discontinue the subject early from the study (Section 5.3). 
In the rare case that a dose with moderate symptoms is assessed as tolerated, follow the guidelines for mild symptoms and provide a brief explanation for the assessment in the subject's source documents.

Severe	
Discuss early discontinuation with the medical monitor. If continuation of study product is considered to be safe, administer a reduced dose at 2 dose levels at the time of the next dose at the study site under medical supervision. If the reduced dose is tolerated, continue that dose level for at least 2 weeks before attempting re-escalation. If the reduced dose is assessed as not tolerated, stop study product dosing and discontinue the subject early from the study (Section 5.3).
 
If the symptoms were associated with a modifiable risk factor that has resolved, the dose may be reduced by 1-2 dose levels at investigator discretion.
 
Stop study product dosing and discontinue the subject early from the study if the subject has anaphylaxis that requires intensive treatment.

Life-threatening	
Stop study product dosing and discontinue the subject early from the study (Section 5.3).

Assess dose tolerability per [Section 8.7.1.1](#).

GI, gastrointestinal.

Appropriate intervention for allergy symptoms associated with a new dose or dose level at the study site or dosing at home will depend on the type and severity of symptoms. The process algorithm for dose adjustments after administration of antihistamines and/or epinephrine for dose-related allergy symptoms, including anaphylaxis, at the study site or at home during up-dosing and maintenance is described in [Table 14](#).

Table 14: Dose Adjustment of Study Product After Treatment With Antihistamines and Epinephrine for Dose-Related Allergy Symptoms During Up-Dosing and Maintenance

Medications	Action
Antihistamines	Continue study product up-dosing if symptoms only require antihistamines. If symptoms during up-dosing at the study site or at home require > 2 doses of antihistamine alone or in combination with other medications, reduce the next dose of study product by 1 or 2 dose levels and give it at the study site under medical supervision. If no symptoms occur at the reduced dose, continue up-dosing for the 2-week dosing interval.
Epinephrine	If epinephrine is required for dose-related allergy symptoms, including anaphylaxis, give the next dose of study product at the study site under medical supervision. The dose should be reduced by 1 or 2 dose levels at the discretion of the investigator based on the type and severity of the symptoms (Figure 3, Table 13). After continuing the reduced dose for a duration of time recommended by the investigator, dose re-escalation at 1 dose level may be attempted at the study site. If epinephrine is administered for severe symptoms, discussion with the medical monitor is required. If epinephrine is administered 3 or more times for an event of dose-related symptoms or anaphylaxis, stop study product dosing and discontinue the subject early from the study (Section 5.3). If epinephrine is given at home, recommend that subjects be taken to the nearest emergency department immediately.

8.7.4 Dose Adjustment of Study Product for Reasons Other Than Allergic Reactions to Study Product

The study product dose level may be continued or reduced, or the dose withheld per investigator judgment in the event of a flare of asthma or atopic disease (eg, atopic dermatitis) not related to study product, or intercurrent illness. In addition, the study product dose level may be temporarily reduced for decreased study product tolerability during menses.

The amount of dose reduction may range from 1 dose level (ie, the previous dose level) to approximately 50% (rounded down to the nearest feasible whole dose) at the discretion of the investigator. The lowest dose level for dose adjustments is 1 mg.

If the dose is reduced for reasons other than allergic reactions to study product, the reduced dose will be given until the subject is fully recovered (ie, baseline status) for at least 3 days, depending on the severity of the illness per investigator assessment, before attempting dose re-escalation at the study site. Treatment for an intercurrent illness or disease should be discontinued before dose re-escalation. However, if the treatment cannot be withdrawn successfully, it may be administered concurrently with study product.

The process of dose re-escalation for reduced doses due to reasons other than allergic reactions will depend on the degree and duration of the dose reduction as described in

Table 15. A dose re-escalation attempt should be made within 4 weeks after a dose reduction.

The study product may also be withheld as part of the treatment for intercurrent adverse events at the discretion of the investigator; dose continuation after temporary withholding will follow the procedure for missed study product doses ([Section 8.7.5](#)).

Study product dosing will stop and the subject will discontinue early from the study ([Section 5.3](#)) if either of the following conditions for dose adjustment are met:

- The dose level cannot be escalated after 3 consecutive failed attempts with at least 2 weeks between each escalation attempt.
- The dose reduction cannot be tolerated after 3 attempts to reduce the dose level.

Table 15: Study Product Dose Re-Escalation After Dose Reduction for Reasons Other Than Allergic Reactions

Duration of Dose Reduction	Action
1-2 consecutive days	Next dose at the previous dose level at home and continue the dose level for 2 weeks.
3-4 consecutive days	Next dose at the previous dose level under medical supervision at the study site and continue the 2-week dosing interval.
5-7 consecutive days	Next dose under medical supervision at the study site at the previous dose level. If re-escalation is tolerated, continue the dose level for at least 2 weeks before attempting re-escalation.
8-14 consecutive days	Next dose under medical supervision at the study site at 1 dose level above. If re-escalation is tolerated, continue the dose level for at least 2 weeks before attempting re-escalation.

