8.7.1.1 Assessment of the Tolerability of a Study Product Dose or Dose Level

The tolerability of a study product dose or dose level will be assessed based on the occurrence of acute allergy symptoms (allergic reactions) after dosing. When multiple symptoms are present, the severity of the most severe symptom will be used to determine whether symptoms are dose limiting and the dose or dose level is tolerated. Possible assessments of symptom severity, dose-limiting symptoms, and dose tolerability are shown in [Table 11](#).

Table 11: Allergy Symptom Severity and Study Product Dose Tolerability

Symptom Severity	Dose-Limiting Symptom	Assessed Tolerability of Dose
None	No	Tolerated
Mild, oropharyngeal symptoms only	No	Tolerated
Mild, meeting tolerability criteria	No	Tolerated
Mild, not meeting tolerability criteria	Yes	Not tolerated
Moderate, with rare exceptions	Yes	Not tolerated
Severe	Yes	Not tolerated
Life-threatening	Yes	Not tolerated

No Symptoms: A study product dose associated with no symptoms will be assessed as tolerated.

Mild symptoms: For a study product dose associated with mild symptoms, investigator assessment is essential in determining if the symptoms are dose limiting. Mild symptoms are not dose limiting if they meet all of the tolerability criteria as follows:

- Are isolated to a single organ system
- Resolve with no medications or with \leq 2 doses of oral antihistamine
- Do not require administration of epinephrine
- Do not worsen in intensity or distribution over time
- Resolve or show definite signs of resolving in under 1 hour
- Do not include objective wheezing

The study product dose is to be considered not tolerated if mild symptoms do not meet the tolerability criteria as follows:

- Occur in 2 or more organ systems
- Require treatment with \geq 3 doses of oral antihistamine or \geq 1 dose of epinephrine
- Progress in severity or distribution over time
- Do not resolve or show definite signs of resolving in under 1 hour
- Include objective wheezing

If a study product dose associated with mild symptoms that do not meet the tolerability criteria is assessed as tolerated by the investigator, an explanation must be provided in the subject's source documents.

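### Read literally, Table 14's antihistamine row conflicts with Table 13 for moderate and not-tolerated mild reactions treated with only 1-2 antihistamine doses during up-dosing: a minor safety-wording inconsistency

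*Protocol*

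**What the plan says.** **Table 14, antihistamine row (Section 8.7.3.2).** The first sentence reads "Continue study product up-dosing if symptoms only require antihistamines". The next sentence supplies the only trigger for a reduction: if symptoms "require > 2 doses of antihistamine alone or in combination with other medications, reduce the next dose of study product" by 1 or 2 levels, at the site. The row mentions neither severity nor tolerability and does not refer to Table 13.

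**Table 14, epinephrine row.** Here the size of the reduction is "at the discretion of the investigator based on the type and severity of the symptoms (Figure 3, Table 13"), so this row does point back to the severity-based rules.

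**Scope of Table 14.** Note 1 to Figure 3 says: "Guidelines for dose adjustment after administration of antihistamines and/or epinephrine for dose-related allergy symptoms of any severity are provided in" Table 14.

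**Table 13.** After a mild reaction whose dose is assessed as not tolerated, "the next dose is to be the previous tolerated dose level and given at the study site". After a moderate reaction the instruction is "Administer the previous tolerated dose of study product at the study site at the time of the next dose". Neither entry depends on what treatment was given.

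**Section 8.7.1.1.** "Mild symptoms are not dose limiting if they meet all of the tolerability criteria as follows", followed by six criteria. Failing any one, for example because symptoms "Occur in 2 or more organ systems", makes the dose not tolerated. Moderate symptoms are not tolerated apart from rare exceptions.

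**The concern.** Table 14 decides by antihistamine count and Table 13 by severity and tolerability. Note 1 to Figure 3 sends antihistamine-treated reactions to Table 14 whatever their severity, so both tables can apply to the same reaction. A moderate reaction that settles after one or two antihistamine doses gets a reduced, supervised dose under Table 13. Under the literal wording of Table 14 the subject simply continues.

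A site that took the row at face value could repeat a dose that the Protocol itself classes as not tolerated, and two sites could handle the same reaction differently. This is a first-in-human study (Section 1.2) in subjects aged 4 to 26 at about 30 sites, so the dosing instructions should not leave room for that.

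**Working it through.** The Protocol states no figure on this point, so the check is a comparison of text.

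**Step 1: which tolerability conditions the row covers.** Section 8.7.1.1 requires all six of these for a mild reaction to be non-dose-limiting:

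| Criterion | Covered by the antihistamine row? |
|---|---|
| Single organ system | No |
| No medication, or at most 2 oral antihistamine doses | Yes, by the trigger above 2 doses |
| No epinephrine | Yes, through the word *only* |
| No worsening | No |
| Resolving in under 1 hour | No |
| No objective wheezing | No |

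The row covers 2, leaving 6 − 2 = 4. It also says nothing about moderate severity. The count describes the wording. It does not measure how often the gap would matter.

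**Step 2: the two tables case by case, during up-dosing.**

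| Reaction | Table 13 | Table 14, read literally | Result |
|---|---|---|---|
| Moderate, 1-2 antihistamine doses | Previous tolerated dose at the site | Continue | Conflict |
| Mild, not tolerated (e.g. two organ systems), 1-2 doses | Previous tolerated level at the site | Continue | Conflict |
| Mild, tolerated, 1-2 doses | Repeat or continue the level; reduction optional if symptoms recur | Continue | No clear conflict |
| Mild or moderate, more than 2 doses | Reduce | Reduce by 1 or 2 levels | Broadly consistent |

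**Step 3: does anything visible settle the order?** No sentence ranks the tables. The reminder to assess tolerability under Section 8.7.1.1 stands beneath Figure 3 and Table 13 but not beneath Table 14. The day-1 counterpart in Table 12 (Section 8.7.3.1) allows escalation to continue after 1 or 2 antihistamine doses only where the symptoms are mild, and Table 14 lacks that qualifier. Table 12 also names antihistamines as a possible first treatment for moderate symptoms that are not worsening, so the combination is realistic. Figure 3 itself is not available in the text reviewed, so its flow cannot be checked.

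**Step 4: where exposure remains.** Section 5.2.3.2 makes home dosing at a new level conditional on tolerating the supervised first dose, so that dose is already protected. Later home doses in the 2-week interval remain. For those, Section 8.7.3.2 requires symptoms to be reported to the site and strongly encourages supervised dosing. That brings the site in before the next dose, but it settles where the dose is given and not its level.

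**The case against.** The strongest reply is that the row does not mean *no reduction*. Its last sentence uses the same expression, continuing up-dosing, for a subject whose dose has just been reduced. The first sentence can therefore mean only that the subject stays in the up-dosing period, and then it does not contradict Table 13. On that reading the trigger above 2 doses is an additional reason to reduce and does not cancel Table 13.

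The surrounding text supports this. Sections 7.2, 8.7.2, 8.7.3.2 and 8.7.6.2 each say that symptomatic treatment supplements dose reduction and does not replace it. Section 8.7.3.2 says severity guides reductions, and the lead-in to Table 14 makes intervention depend on the type and severity of symptoms. Section 8.7.1.1 requires a written explanation whenever a mild reaction that fails the criteria, or a moderate reaction, is called tolerated. Table 14 is also reached from Figure 3, which carries its own tolerability reminder.

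Most of this stands. It shows that the conflict is confined to the literal reading and that Table 13 is very likely meant to control. It does not remove the literal reading: within the row, continuing is set against reducing above 2 doses, so *no reduction at 1-2 doses* is a natural inference, and nothing visible corrects it.

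A reader might go further and infer that the Protocol lets antihistamines stand in for dose reduction, or that Table 14 overrides Table 13. The four sections above say the opposite on the first. On the second, the note to Figure 3 gives Table 14 a scope and no priority.

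**Conclusion.** The inconsistency is real on a literal reading and minor. It affects two groups during up-dosing, moderate reactions and mild reactions assessed as not tolerated, when only 1 or 2 antihistamine doses were given. The intended rule is very likely Table 13. The first dose of each new level is protected by Section 5.2.3.2 and home reactions must be reported, so what remains mainly concerns reactions to home doses.

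The number of reactions affected cannot be derived from the Protocol. A reader might infer some effect on the desensitization response rate. Nothing in the documents supports that, and no sample-size, power or error-rate figure depends on this row. The conclusion assumes that the unseen Figure 3 does not state an order of precedence. If it does, only a missing cross-reference remains.

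**What to change.** Replace the first sentence of the antihistamine row with wording such as: *Continue up-dosing if symptoms need only 1 or 2 doses of antihistamine and the dose is assessed as tolerated (Section 8.7.1.1); if the dose is assessed as not tolerated, adjust it per Table 13.* The explicit cap also removes an overlap inside the row, whose first sentence as it stands could cover more than 2 doses of antihistamine alone.

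Keep the sentence on more than 2 doses unchanged. Do not add a rule that the larger of two reductions applies. That would be a new dosing rule, and it would cut into the discretion the Protocol gives investigators in the epinephrine row of Table 14 and in Table 13 for severe reactions linked to a resolved risk factor.

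The cost is a wording change in the next amendment and a memo to sites, with no extra visits or subjects.
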